1.2 Dose rationale

The doses of PCC and FP selected for the study are the same doses used for the pilot FARES study. There is an absence of a consensus regarding PCC dosing in acquired coagulation factor deficiency; however, the study dose of PCC represents current

recommended dosing for bleeding indications in various settings and is consistent with doses used in other studies in cardiac settings [27, 61, 79, 80]. Moreover, the maximum dose is equal to or lower than doses of PCC that have demonstrated a good safety and tolerability profile in other clinical settings (e.g., factor Xa inhibitor reversal in major bleeding [81-83] and trauma [84]. Of note, neither PCC nor FP will be administered to patients unless they are deemed to be clinically indicated by the ordering physician based on objective clinical criteria that will ensure adherence to best blood management practices.

1.3 Benefit-Risk Statement

Substituting either PCC or FP for the other is not expected to pose any material risks to the participants. Patients will only be included in the trial when their clinicians have ordered coagulation factor replacement for treatment of bleeding according to clinical and laboratory criteria; thus, patients would have received one or the other therapy as part of their routine clinical care. The two coagulation factor replacement therapies, *Octaplex* (the PCC to be used in this study) and FP, are both commonly used therapies for this procedure in many regions, with an expected comparable clinical safety profile. *Octaplex* is currently approved for use in Canada (but not in the United States) for the “treatment of bleeding and perioperative prophylaxis of bleeding in acquired deficiency of prothrombin complex coagulation factors, such as deficiency caused by treatment with vitamin K antagonists, or in case of overdose of vitamin K antagonists, when rapid correction of the deficiency is required” [85]. This approved indication falls within the proposed use in this study. In contrast, in the United States, *Octaplex* is approved under the tradename *Balfaxar* for the urgent reversal of acquired coagulation factor deficiency induced by Vitamin K antagonist (VKA, e.g., warfarin) therapy in adult patients with need for an urgent surgery/invasive procedure.

The experience to date with this PCC has shown a favourable safety profile [81, 82, 86-88]. As discussed, PCC is pathogen-reduced, can be administered quickly and in predictable doses, and has a substantially lower risk of TRALI and TACO compared with FP, making its administration likely to be both safer than, and at least as efficacious as, FP. It is possible that treatment with PCC may not be as effective as FP given that it does not contain the full complement of clotting factors that plasma contains, but the study protocol will allow patients in the PCC group to receive FP if haemostatic control is not achieved after two doses of PCC. By limiting maximal PCC dosing to well within acceptable limits that have been proven safe in other settings [81, 82, 86-88], theoretical risks for thrombotic complications have been mitigated.

1.4 COVID-19 Benefit-Risk Statement

Patients in the LEX-211 study will attend hospital for either emergency or scheduled elective cardiac surgery. The patients will not receive any additional contact with study staff beyond those required for undergoing the surgical procedure. The final postoperative visit will be carried out by phone unless the patient is currently in hospital, in order to reduce contact between the patient and healthcare staff. All surgeries will be carried out using standard safety measures in place at the treatment centres in line with local requirements for COVID-19 risk management. The study therefore does not place patients at any additional risk, since emergency surgical procedures must take place immediately, and elective cardiac surgery likewise cannot be postponed for long periods of time and therefore would go ahead even during the COVID-19 pandemic.

Potential COVID-19 related risks for site and project management will be evaluated in advance and options such as alternative monitoring approaches will be implemented. In addition, for the support of the study processes (e.g., provision of the study medication), only well-established service providers are selected which have strong regional expertise and strict risk and quality guidelines in place, including with regards to potential COVID-19-related risks. The current regulations regarding transport and logistics will be continuously monitored for the countries participating in the study, and flexible solutions and longer lead times will be implemented wherever appropriate.

Property of Octapharma. Do not copy or distribute without written permission.

2 STUDY OBJECTIVES

2.1 Primary Objective

1. To demonstrate that the 4-factor prothrombin complex concentrate (PCC) *Octaplex* is clinically non-inferior to frozen plasma (FP) with respect to haemostatic effectiveness, as measured by the need for post-therapy haemostatic interventions.

2.2 Secondary Objectives

1. To compare global haemostatic response between the *Octaplex* and FP groups, as measured by a composite of the need for post-therapy haemostatic interventions and drop in haemoglobin.
2. To compare the amount of bleeding as measured by the amount of chest tube drainage between the *Octaplex* and FP groups.
3. To compare the incidence of severe to massive bleeding between the *Octaplex* and FP groups.
4. To compare efficacy in terms of the total number of allogeneic blood components transfused between the *Octaplex* and FP groups.
5. To compare efficacy in terms of the incidence and number of individual allogeneic blood components transfused between the *Octaplex* and FP groups.
6. To compare the incidence of use of other coagulation factor products between the *Octaplex* and FP groups.
7. To compare the incidence of other bleeding-related clinical endpoints, i.e., intracerebral haemorrhage, gastrointestinal haemorrhage and surgical re-exploration, between the *Octaplex* and FP groups.
8. To compare the effect of *Octaplex* versus FP administration on the international normalised ratio (INR) between the *Octaplex* and FP groups.
9. To compare the effect of *Octaplex* versus FP administration on other coagulation parameters.
10. To compare time from IMP initiation to arrival in the ICU between the *Octaplex* and FP groups.
11. To compare safety as measured by serious treatment-emergent adverse events (TEAEs) between the *Octaplex* and FP groups.
12. To compare other secondary safety endpoints including duration of mechanical ventilation, duration of intensive care unit (ICU) stay, duration of hospitalisation, incidence of death and days alive and out of hospital between the *Octaplex* and FP groups.

3 INVESTIGATIONAL PLAN

3.1 Primary and Secondary Endpoints

3.1.1 Primary Endpoint

1. Comparison of haemostatic treatment response to *Octaplex* versus FP, defined as 'effective' if no additional haemostatic intervention, such as administration of any systemic haemostatic agents (including platelets, cryoprecipitate, fibrinogen concentrate, activated recombinant factor VII, other coagulation factor products or a second dose of IMP) or any haemostatic interventions (including surgical re-opening for bleeding) is required from 60 minutes to 24 hours after initiation of the first dose of IMP.

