PCC offers a potential alternative to FP for treating bleeding cardiac surgery patients requiring coagulation factor replacement; however, no PCC product is currently approved for this indication in the United States. PCCs contain prothrombin and other enzymatic coagulation factors, the anticoagulant proteins C and S, and small amounts of heparin; thus, they are contraindicated in patients who are allergic to heparin or have a prior history of heparin-induced thrombocytopenia. PCCs are routinely defined as 3-factor (containing factors II, IX and X) or 4-factor (containing factors II, VII, IX and X) formulations [48]. PCCs are purified from human pooled plasma, which is fractionated into cryoprecipitate and cryoprecipitate-free plasma fractions through a process of slow thawing, then eluted from cryoprecipitate-free plasma [48]. The production of PCCs includes numerous pathogen inactivation steps using solvents, detergents, pasteurisation, nanofiltration and vapor-heated treatment [1, 48].

PCCs have several potential advantages over FP. Solvent/detergent treatment and filtering to remove pathogens substantially reduces the risk of transmission of infectious agents with PCCs. Indeed, a Consensus Conference recommended in 2007 that pathogen reduction technologies should be implemented to improve the safety of transfusion when they became available [49]. Unlike FP, PCCs do not require ABO compatibility matching or thawing, and can therefore be prepared and administered more quickly. PCCs are associated with a substantially lower risk of TRALI (due to pooling of the source donor plasma), and also a lower risk of TACO [38] as substantially lower volumes of PCC are required than with FP to achieve dose-equivalence for increasing thrombin generation (for example, in a 70-kg patient, a standard dose of 25 IU/kg PCC would be administered in a volume of 80 mL, whereas a standard dose of 15 mL/kg FP would be administered in a volume of 1000 mL) [47]. Finally, PCCs contain standardised levels of coagulation factors and thus have a more predictable therapeutic effect than FP, whose coagulation factor concentrations vary depending on the characteristics of the donor [50, 51].

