A second dose of IMP can be administered if the patient continues to have at least moderate bleeding and suspected coagulation deficiency (e.g., INR ≥ 1.5) after completion of the first dose. If an order for a second dose of coagulation factors is received within 24 hours after IMP initiation (either from the operating room or in the ICU after surgery), the blood bank/pharmacy technologist will release the IMP as determined by the randomisation schedule up to the maximum allowable dose (*Octaplex* 3000 IU if ≤ 60 kg or 4000 IU if >60 kg; FP 6 U if ≤ 60 kg or 8 U if >60 kg) (a tamper-sealed container will not be used for these orders as clinicians will by now be unblinded).

If further doses of coagulation factors are required after the second dose of IMP, all patients will receive non-IMP FP. That is, for subsequent orders once the maximum dose of IMP has been administered (i.e., 2 doses), or after the 24-hour treatment period has elapsed, the technologist will release FP for both groups (in 1–4 U increments as per the ordering physician); these additional FP units will not be counted as part of the IMP (**Figure 1**).

Transfusion of non-IMP blood components and all haemostatic agents will be according to a standardised transfusion management algorithm (**Figure 2**). Measurements of INR and haemoglobin will be performed at preestablished time points, if not available already. No other aspects of routine clinical care will be modified.

Figure 1: Study Flow¹ FP in 1U increments as per the ordering physician

PCC, prothrombin complex concentrate; FP, frozen plasma; BW, body weight; IU, international units;

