7.2 Efficacy Assessments

7.2.1 Assessments for Primary Efficacy Endpoint

7.2.1.1 *Haemostatic Treatment Response to IMP*

A dichotomous classification of haemostatic effectiveness will be used to assess the primary endpoint of haemostatic treatment response to PCC or FP in bleeding cardiac surgical patients. Treatment will be considered 'effective' if no additional haemostatic intervention is required in the time window from 60 minutes to 24 hours after initiation of the first IMP dose (**Table 3**). The 60-minute time period will allow for the administration of the IMP and establishment of treatment effect. Patients will be assigned a haemostatic treatment response classification of 'ineffective' if their management required haemostatic interventions during the time window from 60 minutes to 24 hours after initiation of the first IMP dose.

Table 3: Objective Criteria for Determination of Haemostatic Treatment Response to IMP

Haemostatic Response	Haemostatic Intervention
Effective	No additional haemostatic interventions ¹ administered between 60 minutes and 24 hours after initiation of infusion ²
Ineffective	Additional haemostatic interventions ¹ administered between 60 minutes and 24 hours after initiation of infusion ²

¹ Administration of any systemic haemostatic agents (including platelets, cryoprecipitate, fibrinogen concentrate, activated recombinant factor VII, other coagulation factor products or a second dose of IMP) or any haemostatic interventions (including surgical re-opening for bleeding).

² The 60-minute period allows for the administration of the IMP and establishment of treatment effect.

Patients categorised as having an 'ineffective' haemostatic treatment response to IMP, due to requiring administration of any haemostatic intervention, including a second dose of IMP, in the time window from 60 minutes to 24 hours after initiation of the first IMP dose, will be considered as treatment failures.

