## 10.4. Sensitivity Analyses

The analysis results for the primary endpoint will be presented in different contexts. This will include those involving the different multiple imputation procedures for missing data, if needed. The analysis of the primary endpoint will be presented for the PPS. Haemostatic treatment response will also be summarized descriptively by study site.

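### The uncounted first hour can hide a failed first dose, possibly more often with PCC, and no planned sensitivity analysis tests this

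*Protocol*

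**What the plan says.** Protocol 3.1.1 defines an effective response as one where no listed haemostatic intervention, a second IMP dose among them, "is required from 60 minutes to 24 hours after initiation of the first dose of IMP". Protocol 3.3.3, Table 3 and 9.1, and SAP 5.1, 10.2 and Appendix 1, use the same window. The gap is deliberate: "The 60-minute time period will allow for the administration of the IMP and establishment of treatment effect" (Protocol 7.2.1).

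On the second dose, Protocol 3.2 says: "A second dose of IMP can be administered if the patient continues to have at least moderate bleeding", together with a suspected coagulation deficiency, "after completion of the first dose". No minimum time from initiation is set.

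On speed, Protocol 1.1 says: "Unlike FP, PCCs do not require ABO compatibility matching or thawing, and can therefore be prepared and administered more quickly". For a 70-kg patient it describes a standard PCC dose as "administered in a volume of 80 mL, whereas a standard dose of 15 mL/kg FP would be administered in a volume of 1000 mL". Protocol 5.5 has PCC given by free-flowing syringe injection; Protocol 5.1.2 leaves plasma infusion to hospital practice.

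On sensitivity analyses, SAP 10.4 offers multiple imputation if needed, a descriptive summary by site, and the following: "The analysis of the primary endpoint will be presented for the PPS". SAP Table 1 scores death or discontinuation before 24 hours as non-response. It starts the window from administration of the first treatment, where every other definition says initiation.

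**The concern.** The primary objective is measured by the need for haemostatic intervention after therapy. A second dose given because bleeding continued after the first is such a need. If it falls inside the first hour and nothing listed follows in the window, the patient is scored as a responder.

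The hour is equal in minutes but need not hold the same amount of treatment in each arm. A PCC patient can finish the first dose, be reassessed and receive the second before 60 minutes. A plasma patient with the same bleeding course may still be receiving the first dose then, and so have the second dose counted. Treating clinicians are unblinded by that point (Protocol 3.2), so the timing of the next product is not protected by blinding. An imbalance of this kind would move the observed difference toward PCC in a non-inferiority comparison.

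**Working it through.** **1. The planned sample size.** Inputs from Protocol 9.1: PCC 70%, FP 65%, margin 0.10, one-sided α 0.025, power at least 90%, Farrington-Manning test; 205 per arm from Protocol 3.3.1.5. The restricted maximum-likelihood rates at the margin are 0.619 (PCC) and 0.719 (FP).

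- Null SD term: √(0.619×0.381 + 0.719×0.281) = 0.662
- Alternative SD term: √(0.70×0.30 + 0.65×0.35) = 0.661
- Power = Φ[(√205 × 0.15 − 1.96 × 0.662) / 0.661] = Φ(1.286) ≈ 90.1%

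The stated 410 reproduces. Simulating the equal-weight inverse normal combination with stages of 200 and 210 gives 90.2%.

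**2. Can a second PCC dose fit in the hour?** Protocol 5.2 reconstitutes 500 IU in 20 mL and 1000 IU in 40 mL, so the trial doses of 1500 and 2000 IU are 60 and 80 mL. Nothing in the documents stops 60–80 mL by syringe, reassessment and a second dose from falling within 60 minutes. No infusion time is given for either product. Thawing and matching of plasma precede initiation and do not affect this clock; volume and route do.

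**3. Who is hidden.** A patient is hidden only if all of these hold: an intervention occurs in 0–60 minutes, no listed intervention follows between 60 minutes and 24 hours, and the patient neither dies nor discontinues before 24 hours.

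**4. Where hidden events appear elsewhere.**

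| First-hour event | Seen in |
|---|---|
| Platelets, cryoprecipitate, fibrinogen concentrate, rFVIIa | S6–S9 as applicable and bleeding class (S3), timed from IMP initiation but pooled over at least 24 h |
| Re-exploration | S3, S12, pooled over 24 h |
| Second plasma dose | S4 (all FP), exposure tables |
| Second PCC dose | exposure tables only (SAP 7.2: dose and frequency, not timing) |

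Global response (S1) shares the primary window, so it has the same gap. An early second PCC dose enters no efficacy endpoint.

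**5. Effect on the conclusion.** Let d be the share of PCC patients who are hidden minus the same share in FP. The documents give no value for d, so it is an assumption. Suppose the true 0–24 hour difference is exactly −10 points (PCC 55%, FP 65%). The planned window then sees −10 + d.

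- SE = √[(0.55×0.45 + 0.65×0.35)/205] = √(0.475/205) = 0.0481
- Chance of declaring non-inferiority = 1 − Φ(1.96 − d/0.0481)

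| d (points) | 1.96 − d/0.0481 | Chance |
|---|---|---|
| −4 | 2.79 | 0.3% |
| −2 | 2.38 | 0.9% |
| 0 | 1.96 | 2.5% |
| +2 | 1.54 | 6.1% |
| +4 | 1.13 | 13% |

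Simulation of the two-stage test agrees: 2.6% at d = 0 and 6.3% at d = +2. With 800 patients in stage 2, d = +2 gives 9.1%.

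**6. If early interventions were counted.** Starting from 70% versus 65% and 205 per arm, losing 5 points in both arms leaves power at 88.2%. Losing 2 points in PCC only leaves 79.8%; losing 5 points in FP only raises it to 98.9%. An equal early rate does little; a difference between arms is what matters.

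**The case against.** The strongest reply is that the direction is not shown. Volume is not time, and the 1000 mL figure is a 15 mL/kg illustration rather than the trial's 3–4 units; the pilot's plasma median was 12.5 mL/kg. Platelets or fibrinogen given while plasma is still running, or before it has acted, would hide plasma failures instead. This stands, and it is why the range above runs both ways.

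Second, the null hypothesis in Protocol 9.2 and SAP 10.2 concerns response from 60 minutes to 24 hours. A reader might infer that the planned test exceeds its 2.5% level. The documents do not support that: the figures above answer a 0–24 hour question which the protocol does not pose.

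Third, early second doses are constrained. They need a completed first dose, continuing moderate bleeding, suspected deficiency and a new order, and the mandated post-dose INR is due at 60 ± 15 minutes. This limits the opportunity without closing it.

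Fourth, the gap has a stated reason and the pilot used the same window, so planning rates match the endpoint. That is true, but the reason given is time for administration, which is where the products differ, and pilot rates with the same gap cannot show what lies in it.

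**Conclusion.** The point holds in a limited form. First-hour interventions, including a second IMP dose, do not by themselves count as failures. The hour can hide a failed first dose more often in the PCC arm, and no planned sensitivity analysis of the primary endpoint examines this. The main blind spot is an early second PCC dose; early non-IMP products and re-exploration are partly visible in secondary endpoints.

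A reader might go further and conclude that the endpoint is biased toward PCC. The documents do not establish that, because they give neither infusion durations nor first-hour event rates by arm. What they support is that a modest imbalance would matter to the 0–24 hour reading: about 6.1% instead of 2.5% for a net 2 points against FP, and about 0.9% for 2 points the other way. These figures assume a true difference at the margin, 205 per arm and an assumed net excess. The unknown size and sign are a reason to make the check, not to change the primary endpoint.

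**What to change.** Leave the primary endpoint, sample size and clinical rules as they are. Add to SAP 10.4:

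1. The primary test repeated with any second IMP dose, from initiation of the first dose to 24 hours, also counted as a failure.
2. A table by arm of first-infusion duration, and of second doses and other listed interventions in the first 60 minutes.

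A run counting all listed interventions from 0 to 24 hours may be added as supportive only. The transfusion algorithm (Protocol Figure 2) allows therapies to be combined in life-threatening bleeding, so that run also scores concurrent therapy as failure.

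Reconcile SAP Table 1 with the other definitions on whether the window starts at administration or initiation. If administration were read as the end of infusion, the window would open later in the slower arm.

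The cost is one or two extra runs of the planned test and one table. IMP start and end times and all haemostatic therapies are already collected (Protocol 6.1.3, SAP 9). The result may be less favourable to either arm.

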3.1.2 Secondary Endpoints

1. Comparison of global haemostatic response to *Octaplex* versus FP, defined as 'positive' if no additional haemostatic intervention (as per the primary endpoint) is required and haemoglobin levels decrease by <30% (after accounting for red cell transfusions) from 60 minutes to 24 hours after initiation of the first dose of IMP.
2. Comparison of the total amount of chest tube drainage at 12 and 24 hours after chest closure between the *Octaplex* and FP groups.
3. Comparison of the incidence of severe to massive bleeding, using a modification of the universal definition of perioperative bleeding (UDPB) in cardiac surgery [89] and its individual components during the first 24 hours after start of surgery, after the end of CPB and after IMP initiation, between the *Octaplex* and FP groups.
4. Comparison of the mean number of total allogeneic blood components – including red cells, platelets and all (IMP and non-IMP) FP – administered during the first 24 hours after the end of CPB, between the *Octaplex* and FP groups.
5. Comparison of the mean number of total non-IMP allogeneic blood components – including red cells, platelets and non-IMP FP – administered during the first 24 hours after the end of CPB, between the *Octaplex* and FP groups.
6. Comparison of the mean number of total non-IMP allogeneic blood components – including red cells, platelets, cryoprecipitate and non-IMP FP – administered during the first 24 hours and 7 days after IMP initiation, between the *Octaplex* and FP groups.
7. Comparison of the mean number of individual allogeneic blood components – including red cells, platelets, cryoprecipitate and non-IMP FP – administered during the first 24 hours and 7 days after the start of surgery, after the end of CPB and after IMP initiation, between the *Octaplex* and FP groups.
8. Comparison of the incidence of transfusion of individual allogeneic blood components – including red cells, platelets, cryoprecipitate and non-IMP FP – during the first 24 hours and 7 days after the start of surgery, after the end of CPB and after IMP initiation, between the *Octaplex* and FP group.
9. Comparison of the incidence of administration of non-IMP coagulation factor products – including fibrinogen concentrate and activated recombinant factor VII –

during the first 24 hours and 7 days after the start of surgery, after the end of CPB and after IMP initiation, between the *Octaplex* and FP groups.

10. Comparison of the incidence of intracerebral haemorrhage during the first 24 hours after start of surgery, after the end of CPB and after IMP initiation between the *Octaplex* and FP groups.
11. Comparison of the incidence of gastrointestinal haemorrhage during the first 24 hours after start of surgery, after the end of CPB and after IMP initiation between the *Octaplex* and FP groups.
12. Comparison of the incidence of surgical re-exploration during the first 24 hours after start of surgery, after the end of CPB and after IMP initiation between the *Octaplex* and FP groups.
13. Comparison of the change in INR, from within 30 minutes before to within 60 minutes after the initiation of IMP administration, between the *Octaplex* and FP groups; INR reduction will be considered successful if the magnitude of the reduction is >1.0 or the post-treatment level drops below 1.5.
14. Comparison of the changes in other coagulation parameters, including PT, aPTT, fibrinogen activity, ROTEM EXTEM CT and MCF, ROTEM FIBTEM MCF and platelets, from within 75 minutes before to within 75 minutes after the initiation of IMP administration, between the *Octaplex* and FP groups.
15. Comparison of time elapsed from initiation of the first dose of IMP to arrival into the ICU between the *Octaplex* and FP groups.

